The KCCQ, SF-12, and EQ-5D Questionnaires will be completed by the patient to assess QOL. Data regarding completeness of QOL data collection and reasons for missing responses to questionnaires will be collected on the QOL Case Report Form.

Vital Status Check

At 36, 48 and 60 months (\pm 60 days) post randomization

The patient's vital status will be collected via telephone or a review of medical records.

Cost

Direct costing data for all randomized patients (from US sites) will be obtained by the DCC at the conclusion of the trial.

Event Driven Data Collection

Follow-Up Surgical Procedures

Event Driven

All operations following the initial study defined surgical intervention must be reported on the surgical procedure form within 48 hours of the knowledge of the event. If the operation is to address a complication, the coordinator must also complete an AE report. All intra-operative transfusion requirements must be documented. All follow-up surgical procedures will be recorded through month 24.

Adverse Events

Event Driven

Detailed information regarding AEs will be recorded at the time an AE occurs.

Investigators will be asked to make a judgment as to the seriousness and relationship of the event to the surgical intervention. All AEs will be recorded through month 24.

Re-Hospitalizations

Event driven

All ED visits (of any duration) and re-hospitalizations (>24 hours for any reason) must be reported on the Re-Hospitalization Form. This form collects limited information about hospital procedures, LOS, days in ICU, and discharge if applicable, as well as patient condition and disposition for each hospitalization. All re-hospitalizations will be recorded through month 24.

Outpatient Intervention

Event driven within 48 hours of knowledge of event

All outpatient procedures following the index hospitalization must be reported on the surgical procedure form within 48 hours of the knowledge of the event. If the intervention is to address a complication, the coordinator must also complete an AE report. All outpatient interventions will be recorded through month 24.

Missed Visit Assessment

Event Driven

If a patient is unable to return for follow-up before the closure of a study visit window, a missed visit assessment that captures the reason for missing the visit must be recorded on the protocol deviation form.

Mortality

Event Driven within 24 hours of knowledge of event

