Hospital length of stay and days in Intensive Care: We will compare hospital LOS and days spent in ICU between treatment groups, separately by region (North America and Germany). A Wilcoxon Rank-Sum test will be used to test for differences within each geographic subgroup.

Hospital readmission: Rates of all-cause hospitalizations and rates of cardiovascular and heart failure specific hospitalizations, both within 30 days and within two years will be compared using Poisson regression.

Costs and Cost-Effectiveness

Cost

Cost will be calculated by converting charges to cost using institution specific Ratio-of-Cost-to-Charges (RCCs). Institution-specific cost reports will be used to calculate RCCs for each major resource category. Cost data will only be collected in the North American sites. Costing data will be compared by Student's t test after log transformation.

Independent predictors of cost, including baseline factors, operative factors and postoperative events, will be determined by multivariate regression analysis.

Cost-Effectiveness

The primary objective of the CEA is to estimate the incremental CE ratio (ICER) of the intervention under investigation as compared to the study-defined alternative. This ratio measures the ratio of the difference in costs and outcomes between the two study arms, with outcomes measured as quality-adjusted life-years (QALYs). QALYs reflect an individual's preference for both quantity and QOL in a single measure that facilitates comparisons across diverse treatment modalities. We will also compute net health benefits (NHB) as an alternative way of looking at cost-effectiveness. This parameter compares the incremental effectiveness of an intervention with the minimum health effect

that society would demand in return for the investment; i.e., with the health produced by investing at the societal ceiling cost-effectiveness ratio (CR).

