5.2.6 Hospitalizations

- Index hospitalization LOS and ICU days
- All-cause readmissions and readmissions for heart failure and TR re-operation through the first 30 days following surgery and through 24 months post-randomization

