6. STATISTICAL METHODOLOGY

6.1 General Principles

Study day will be calculated from the reference start date, and will be used to show the study days of assessments and events. Reference start date is defined as the date of randomization unless otherwise specified. In analyses of index length of stay, index ICU days, peri-operative (30 day) mortality, and peri-operative (30 day) readmissions the reference date is

the date of surgery. In the situation where the event date is partial or missing, study day, and any corresponding durations are to appear partial or missing in listings. If a missing event date, such as a discharge date for a hospital readmission, is necessary to calculate patient-time at risk, the missing event date will be imputed using the median length observed for similar events.

Continuous variables will be summarized using the following descriptive statistics: number of non-missing values, means, standard deviations, medians, interquartile range, maximum, and minimum. Categorical variables will be summarized using number of non-missing values, counts and percentages.

Rates of events will be calculated as the ratio of the total number of events recorded divided by the total patient-time. Total patient-time will be calculated by summing the time (in study time units, e.g., days, months or years) that patients were at risk for a specific event from the reference time point until either study exit or the end of the time period of interest. Rates and 95% confidence intervals will be reported.

Time-to-event variables will be summarized using the Kaplan-Meier method or, in the presence of competing risk, the Gray method (Gray, 1988).

For any variable measured at multiple points in time, change from baseline will be calculated as the difference between the value of the variable at a specific point in time (e.g. 1 year) minus the baseline value. Relative change from baseline will be calculated as the value of a parameter at a specific point in time minus the baseline value of the parameter divided by the baseline value of the parameter. Percent change will be calculated as the relative change multiplied by 100.

All hypothesis testing will be conducted at the 0.05 two-sided significance level unless otherwise specified. P-values will be rounded to three decimal places. P-values less than 0.001 will be reported as <0.001 in tables. P-values greater than 0.999 will be reported as >0.999.

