Should any of the statistical methods proposed prove unsuitable during data analysis, more appropriate methods will be used. These include data transformation (for example to a logarithmic scale) to satisfy model assumptions such as normally distributed residuals with constant variance, the application of non-parametric techniques or the use of a different link function or modeling technique.

Additional ad-hoc analyses may be conducted as deemed appropriate.

All analyses will be conducted using SAS V9.4 or higher.

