6.5.2.6 Hospitalizations

Index hospitalization length of stay and days in Intensive Care: We will compare post-surgery hospital LOS and days spent in ICU between treatment groups, separately by region (North America and Germany). A Wilcoxon Rank-Sum test will be used to test for differences within each geographic subgroup.

Perioperative readmission by 30 days: The distribution of the incidence of all-cause readmission, cardiovascular readmission, heart failure readmission, and TR re-operation by 30 days post-surgery will be presented for each randomization arm and compared using chi-squared tests.

Hospital readmission by 2 years: Rates of all-cause hospitalizations and rates of

cardiovascular and heart failure specific hospitalizations, within two years of randomization will be compared using Poisson regression.

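### Two-year readmission rates count repeat admissions but are compared by Poisson regression with no prespecified allowance for overdispersion

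*SAP*

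**What the plan says.** SAP 6.5.2.6 (Hospital readmission by 2 years) states that rates of all-cause and "cardiovascular and heart failure specific hospitalizations, within two years of randomization will be compared using Poisson regression". The protocol's Hospital readmission paragraph, under Analyses of Secondary Endpoints, says the same rates "both within 30 days and within two years will be compared using Poisson regression". The SAP handles the 30-day comparison separately, with chi-squared tests on incidence, so only the two-year comparison is at issue here.

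Two other passages show that repeat admissions count:
- Protocol, Re-Hospitalizations: "All re-hospitalizations will be recorded through month 24".
- SAP 6.1: "Rates of events will be calculated as the ratio of the total number of events recorded divided by the total patient-time".

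The result is used for inference. SAP 5.2.6 lists "All-cause readmissions and readmissions for heart failure and TR re-operation through the first 30 days following surgery and through 24 months post-randomization" as a secondary endpoint. SAP 6.1 adds "All hypothesis testing will be conducted at the 0.05 two-sided significance level unless otherwise specified" and "Rates and 95% confidence intervals will be reported".

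Neither document mentions overdispersion, a scale parameter, a robust variance, a negative binomial model or a recurrent-event model. The nearest text is the general clause in SAP 6.1: "Should any of the statistical methods proposed prove unsuitable during data analysis, more appropriate methods will be used".

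**The concern.** Poisson regression with its default standard error assumes that the variance of the patient counts equals their mean. That fits if all patients in an arm share the same underlying readmission rate and admissions occur independently. Where some patients are readmitted repeatedly and many not at all, the variance exceeds the mean. The rate ratio is still estimated sensibly, but its standard error is too small.

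A between-arm difference in readmissions could then be declared significant at 0.05 when it reflects a few patients with many admissions. The problem grows with event frequency, so it matters most for all-cause readmission and little for rare admission types. The same gap applies in SAP 6.5.2.5 to serious adverse event types that can recur in one patient, with little effect where they are rare.

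**Working it through.** The documents give no readmission rate, dispersion, power or interval width, so there is no figure of the plan's own to reproduce.

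**Inputs from the documents.** 400 patients randomized 1:1, hence 200 per arm (SAP 6.5.1.1); two-sided 0.05 (SAP 6.1); all events counted over patient-time (SAP 6.1).

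**Assumed inputs.** Mean two-year admissions per patient μ, and between-patient (frailty) variance k. Counts are gamma-Poisson, so Var = μ(1 + kμ). There is no true treatment effect.

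**Formulas.**
- Poisson SE of the log rate ratio ≈ √(2 / (200μ)).
- True SE = √(1 + kμ) × Poisson SE.
- Actual type I error of the nominal 5% test = 2[1 − Φ(1.96 / √(1 + kμ))].

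**Numbers put in.**
- μ = 0.4, k = 1: √1.4 = 1.18, giving about 9.8%.
- μ = 0.8, k = 2: √2.6 = 1.61, giving about 22.4%.
- μ = 0.6, k = 1: Poisson SE = √(2/120) = 0.129, so the plain 95% interval multiplies and divides the rate ratio by exp(1.96 × 0.129) = 1.29. The true SE is √1.6 = 1.265 times larger, so the factor should be 1.38.

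**Simulation.** 40,000 replicates per cell, full follow-up, Wald test on the log rate ratio at 1.96. The first four result columns are rejection rates of plain Poisson. The fifth is the range for a patient-level sandwich variance on the same data at k = 0.5 to 2. The last is the mean ratio of robust to plain SE at k = 0.5 / 1 / 2.

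| μ | k = 0 | k = 0.5 | k = 1 | k = 2 | Robust | SE ratio |
|---|---|---|---|---|---|---|
| 0.05 | 4.1% | 4.4% | 4.4% | 4.9% | 4.0–4.1% | not tabulated |
| 0.1 | 4.5% | 4.9% | 5.7% | 6.6% | 4.6–4.8% | 1.02 / 1.04 / 1.08 |
| 0.4 | 4.9% | 7.1% | 9.7% | 14.2% | 5.0–5.3% | 1.09 / 1.17 / 1.32 |
| 0.8 | 5.1% | 9.7% | 14.0% | 22.5% | 5.0–5.4% | 1.18 / 1.33 / 1.59 |

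The simulated 9.7% and 22.5% agree with the formula's 9.8% and 22.4%.

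**Checks.**
- A separate simulation (20,000 replicates per cell; μ = 0.3, 0.6 and 1.0) gave 6.4% to 25.6% for plain Poisson over k = 0.5 to 2, and 4.8% to 4.9% at k = 0. The robust variance gave 4.9% to 5.4% throughout.
- With an assumed 10% of patients leaving at a uniform time and a patient-time offset, plain Poisson barely changed: 5.0% to 6.7% at μ = 0.1, 7.0% to 14.2% at 0.4, 9.5% to 22.0% at 0.8. The sandwich gave 4.7% to 5.6%.
- Fitted models (1,000 replicates; μ = 0.4 and 0.8, k = 0.5 and 2) gave 5.4% to 5.6% for negative binomial, 5.5% to 5.8% for robust Poisson and 7.5% to 21.8% for plain Poisson.

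**The case against.** The strongest reply is that this is an omission and not a stated error. SAP 6.5.2.6 names a model and is silent on the variance; Poisson regression with a sandwich variance would comply with it as written. The protocol ties intervals to the Poisson distribution only for adverse events, and the matching SAP text (6.5.2.5) does not repeat that. SAP 6.1 allows a different modeling technique if a method proves unsuitable, which would cover a negative binomial model. The SAP's purpose section allows revisions before data lock and requires unplanned analyses to be labelled as such.

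This limits the risk but does not remove it. The SAP 6.1 clause has no trigger, names no method for counts and takes effect during data analysis, in a trial where neither patients nor investigators are blinded. Unless a variance is named, the software default is the natural reading.

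A second reply is that the size is entirely assumed. That stands. The protocol describes a fairly low two-year clinical event rate and expects about 15% MACCE on mitral surgery alone, with death and stroke included. That suggests infrequent heart failure admissions, although repeats could raise the mean. At μ = 0.15 the formula gives roughly 6% to 9% for k = 0.5 to 2, so the effect on heart failure readmission is probably small. All-cause readmission could reach the higher rows, but the documents give no rate for it.

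It is also true that SAP 6.5.2.6 promises no rate-ratio interval; SAP 6.5.2.5 does so for adverse events only. The 0.05 test does apply to readmissions, and it depends on the same standard error.

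**Conclusion.** The concern holds. The plan counts repeat admissions, compares them by Poisson regression and prespecifies no protection against overdispersion. If patients differ in readmission risk, plain Poisson standard errors are too small. With 200 per arm and assumed k of 0.5 to 2, the illustration runs from no inflation at 0.05 admissions per patient to type I error of 9.7% to 22.5% at 0.8. If patients do not differ in risk, nothing is lost by the current method. The actual size cannot be determined from the documents.

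This is one of several secondary resource-use comparisons. The primary analysis and the SAP's 30-day chi-squared comparison are unaffected. The change is worth making because it is cheap and protects a tested endpoint.

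**What to change.** In SAP 6.5.2.6, prespecify for two-year all-cause, cardiovascular and heart failure readmissions either Poisson regression with a patient-level robust (sandwich) variance and a log patient-time offset, or negative binomial regression with the same offset. Name one of the two as the reported analysis, so that the choice does not remain open. The robust Poisson version keeps the model already named in both documents. Take the test and the rate-ratio confidence interval from that model. Apply the same rule in SAP 6.5.2.5 to serious adverse event types that can recur.

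The cost is one or two sentences of SAP text before data lock and one statement in the same SAS procedure (REPEATED by patient, or DIST=NEGBIN), with no new data. When counts are overdispersed, intervals on the log scale become about 1.1 to 1.6 times wider at means of 0.4 to 0.8, with less apparent power. When there is no heterogeneity the robust and plain intervals agree (width ratio 1.00).

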6.5.2.7 Costs and Cost-Effectiveness

Cost: Cost will be calculated by converting charges to cost using institution specific Ratio-of-Cost-to-Charges (RCCs). Institution-specific cost reports will be used to calculate RCCs for each major resource category. Cost data will only be collected in the North American sites. Costing data will be compared by Student's t test after log transformation. Independent predictors of cost, including baseline factors, operative factors and postoperative events, will be determined by multivariate regression analysis.

Cost-Effectiveness: The primary objective of the CEA is to estimate the incremental CE ratio (ICER) of the intervention under investigation as compared to the study-defined alternative. This ratio measures the ratio of the difference in costs and outcomes between the two study arms, with outcomes measured as quality-adjusted life-years (QALYs). QALYs reflect an individual's preference for both quantity and QOL in a single measure that facilitates comparisons across diverse treatment modalities. We will also compute net health benefits (NHB) as an alternative way of looking at cost-effectiveness. This parameter compares the incremental effectiveness of an intervention with the minimum health effect that society would demand in return for the investment; i.e., with the health produced by investing at the societal ceiling cost-effectiveness ratio (CR).

Costs will be estimated as discounted incremental health care costs, and effectiveness will be measured as the discounted increment in quality-adjusted life years. A secondary objective will be to identify disease- and patient-related factors that predict high costs of care following the intervention. All CE ratios will be reported with probability intervals to reflect the level of uncertainty in the clinical estimates used in the model and the underlying economic assumptions. We anticipate that the distribution of costs will be skewed to the right. If this violates the assumption of normality, we will modify the method using the nonparametric Bayesian bootstrap. We will use standard discount rates for both QALYs and costs.

We will calculate the ICER based on actual trial data and also develop a model to project long-term cost-effectiveness. Sensitivity analyses will be performed to estimate several sources of uncertainty, including sampling variation and variations in discount rates.

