The change in QOL from baseline will be measured, using the disease-specific KCCQ score, the SF-12 general health status index, and EQ-5D measures of health state preference from the individual and societal perspective. The KCCQ is a widely used tool in heart failure populations. The SF-12 is a general health status measure. This instrument examines 8 quality of life dimensions (physical activity, social activity, role/physical, body pain, general mental health, role/emotional, vitality and general health perception). The EQ-5D is a standardized instrument for measuring health-related quality of life. This questionnaire provides a simple descriptive profile that consists of 5 dimensions. The 5 domains are anxiety/depression, pain/discomfort, usual activities, self-care, and mobility. The instrument also has a self-assessment of health status.

For this trial, the SF-12, EQ-5D, and KCCQ are available in English, Spanish, French and German. Inability to read and complete these instruments in the available languages does not preclude a patient from enrollment in the trial (a family member may assist in completing the QOL questionnaires).

Survival

Perioperative and all-cause mortality over 60 months will be assessed.

Hospitalizations

Length of Index Hospitalization

Overall length of stay (LOS) for the index hospitalization will be measured (and broken down by days spent in the ICU versus days spent on telemetry and regular floors). LOS will be measured as time from index surgery to discharge. In addition, we will capture discharge location.

Readmission and Reoperations

Readmission rates will be calculated for the first 30 days following intervention and through 24 months post-randomization. Hospitalizations will be classified for all causes, including cardiovascular and heart failure readmissions and readmissions for TR operation. Classification of a readmission as heart failure related requires *at least 2* out of the following signs and symptoms of acute decompensated heart failure:

- Dyspnea felt related to heart failure
- Treatment with intravenous diuretic, vasodilator or inotropic therapy
- X-ray evidence of pulmonary edema or pulmonary vascular congestion
- Rales on physical exam
- PCWP or LVEDP > 18 mmHg

All readmissions will be classified by the investigator and adjudicated by the EAC.

All re-operations and re-operation for TR in particular will be recorded through 24 months post-randomization. Freedom from re-operation will be analyzed.

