Economic Measures

Inpatient costs will be measured through the collection of hospital billing and resource utilization information. In addition to index hospitalization costs, costs associated with subsequent readmissions will also be included in the study. Patients will also be asked at each follow-up visit if they have been hospitalized at another hospital and if yes for how long.

For those institutions who participate in Vizient (formerly the University Healthsystems Consortium [UHC]), hospital costs and resource utilization data will be collected. Vizient works with academic medical centers around the country to collect and warehouse clinical, safety, operational and financial data. These data are used to compare performance among peer hospitals and identify best practice patterns. Participating centers will provide unique trial information and the dates of participation in the trial to Vizient who will provide a de-identified data set of the financial data for the trial to the investigators for analysis.

For institutions who do not participate in Vizient, hospital billing data from the UB-92 form will be collected in a de-identified manner from the institutional billing departments. As hospitalization practices differ substantially and detailed accounting data are unavailable for the participating Canadian and German centers, the cost and cost-effectiveness analysis will be restricted to US centers only.

Safety

Adverse Events

Please refer to the CTSN Clinical and Adverse Event Reporting and Adjudication Procedures guidance document for general reporting procedures and guidance on the determination of intervention-expected AEs.

Specific Adverse Event Definitions

AV Conduction Block leading to Permanent Pacemaker Placement

See “Cardiac Arrhythmias” below

New-onset Post-Operative Atrial Fibrillation

See “Cardiac Arrhythmias” below

Bleeding

A bleeding event is defined by any one of the following:

- Transfusion of > 5 units RBC within the first 24 hours following surgery
- Death due to hemorrhage
- Re-operation for hemorrhage or tamponade

NOTE: Hemorrhagic stroke is considered a neurological event and not as a separate bleeding event.

Cardiac Arrhythmias

Any documented arrhythmia that *results in clinical compromise* (e.g., hemodynamic compromise, oliguria, pre-syncope or syncope) that requires hospitalization or requires a physician visit or occurs during a hospital stay.

Cardiac arrhythmias are classified as follows:

- Cardiac arrest

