A patient's frailty status will be assessed through the use of the Gait Speed assessment (see [Appendix V](#)). The assessment averages the time it takes a patient to walk 5 meters during three separate attempts.

New York Heart Association Classification (NYHA)

Within 60 days prior to randomization

The presence of heart failure will be assessed, and when present, classified according to the NYHA scale. NYHA classification will be determined by investigative center personnel delegated to perform this assessment and documented on either the New York Heart Association Classification form or in the body of the medical record. The NYHA classification scheme is detailed in [Appendix III](#).

Medications

Within 60 days prior to randomization

This form captures current medications at one pre-operative time point.

Physical Examination

Within 60 days prior to randomization

This form captures the comprehensive physical examination including vital signs, cardiopulmonary examination, abdominal examination, and anthropometrics (height, weight).

Quality of Life

Within 60 days prior to randomization

The KCCQ, SF-12, and EQ-5D questionnaires will be completed by the patient to assess QOL. Data regarding completeness of QOL data collection and reasons for missing responses to questionnaires will be collected on the QOL Checklist.

Laboratory Assessment

Within 60 days prior to randomization

- Hematology, including white blood cell ($10^3/\mu L$), Hemoglobin (g/dL), Hematocrit (%), Platelet count ($10^3/\mu L$)
- Coagulation profile, including prothrombin time (PT/sec), partial thromboplastin time (PTT/sec), International Normalized Ratio (INR)
- Blood chemistries, including sodium (mM/L), potassium (mM/L), blood urea nitrogen (BUN, mg/dL), creatinine (mg/dL)
- Liver function tests, including total bilirubin (mg/dL), alanine aminotransferase (ALT, U/L), aspartate aminotransferase (AST, U/L), albumin (g/dL).

At time of randomization

- Urine or serum beta HCG (lIU/L) is required for women who have the potential to become pregnant

Randomization Eligibility

Prior to randomization

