5.2.3 Quality of Life

- SF-12 at 6, 12, 18 and 24 months post-randomization.
- KCCQ at 6, 12, 18 and 24 months post-randomization.
- EQ-5D at 6, 12, 18 and 24 months post-randomization.

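### The QALY increment is planned as a difference between arms with no stated adjustment for baseline EQ-5D; adjusting for it is a free gain in precision for a secondary economic endpoint.

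*SAP*

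**What the plan says.** SAP 6.5.2.7 (Costs and Cost-Effectiveness) and the matching protocol section plan an incremental cost-effectiveness ratio (ICER) and a net health benefit, with QALYs as the outcome. On the effect side: "effectiveness will be measured as the discounted increment in quality-adjusted life years". On the contrast: "This ratio measures the ratio of the difference in costs and outcomes between the two study arms". On discounting: "We will use standard discount rates for both QALYs and costs", with no rate given. Regression is planned in that section only for predictors of cost. The sensitivity analyses it names are sampling variation and discount rates.

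EQ-5D is on the schedule before surgery. In the protocol's Screening and Baseline section, within 60 days before randomization, "The KCCQ, SF-12, and EQ-5D questionnaires will be completed by the patient to assess QOL". Follow-up in SAP 5.2.3 is "EQ-5D at 6, 12, 18 and 24 months post-randomization". The protocol's Quality of Life definition is the nearest either document comes to naming the QALY instrument. It refers to "EQ-5D measures of health state preference from the individual and societal perspective".

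The population is described in two ways. Protocol, Economic Measures: "the cost and cost-effectiveness analysis will be restricted to US centers only". SAP 6.5.2.7, like the protocol's own cost analysis text: "Cost data will only be collected in the North American sites".

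**The concern.** A patient's baseline utility predicts later utilities. If the arms differ by chance at baseline, an unadjusted QALY difference carries part of that gap into the ICER denominator and the net health benefit. The bootstrap and the planned probability intervals describe the spread of the estimate but do not re-centre it. Randomization is stratified by TR severity and center, not by EQ-5D, and the analysis set is a subset of the 400 whose size is not stated.

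Nothing elsewhere in the plan supplies the adjustment:

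- SAP 6.5.1.4 adjusts for covariates that differ at the 0.01 level and are substantively large, but only in a secondary analysis of the primary endpoint.
- SAP 6.5.2.3 models quality of life from treatment and time. It names no baseline score as a covariate and yields no QALY increment.
- Change from baseline is defined for repeated measures (SAP 6.1), not for QALYs.

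At stake are the precision and the conditional accuracy of one secondary economic estimate. If adjustment is left open, it could also be decided after the imbalance is known.

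**Working it through.** **The plan's own figure.** There is none to reproduce. Neither document gives an expected QALY difference, an EQ-5D SD, a between-visit correlation or the number of patients in the economic analysis. The trial's sample size rests on the primary endpoint and does not bear on this point.

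**From the documents.** EQ-5D at 0, 6, 12, 18 and 24 months; 1:1 allocation; a subset of 400 patients.

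**Assumed.** QALYs are the area under the EQ-5D curve by linear interpolation. This is an inference, but with no EQ-5D between baseline and 6 months such an area needs the baseline value for the first half-year. Also assumed: 100 patients per arm, SD 0.15-0.20, equal correlation ρ of 0.3-0.7 between visits.

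**Step 1, weights.** The trapezoid rule over two years gives 0.25, 0.5, 0.5, 0.5 and 0.25 year (sum 2.0). Baseline enters directly with weight 0.25 year (0.249 if discounted at an assumed 3%).

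**Step 2, carry-over without deaths or a ceiling.** Shift per unit of baseline imbalance = 0.25 + ρ × 1.75. Variance of a patient's QALY, in units of SD², = 0.875(1 − ρ) + 4ρ, where 0.875 is the sum of squared weights. R² = carry-over² / variance. Reduction in standard error = 1 − √(1 − R²).

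| ρ | Carry-over | Variance | R² | SE reduction |
|---|---|---|---|---|
| 0.3 | 0.775 | 1.8125 | 0.331 | 18% |
| 0.5 | 1.125 | 2.4375 | 0.519 | 31% |
| 0.7 | 1.475 | 3.0625 | 0.710 | 46% |

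The standard error of the baseline imbalance is SD × √(2/100). With SD 0.20 this is 0.028, so a one-SE imbalance shifts the increment by 0.022, 0.032 and 0.042 QALY at the three correlations. Discounting at 3% changes the carry-over only slightly (0.757, 1.095 and 1.434).

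**Step 3, check by simulation.** 20,000 null trials were run (200 patients, SD 0.20, ρ 0.5). The unadjusted difference averaged 0.000, so it is unbiased overall. Its slope on the baseline imbalance was 1.125. In trials with an imbalance near +0.03 it averaged +0.032 QALY, against −0.001 after adjustment. The standard error was 0.044 unadjusted and 0.030 adjusted.

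**Step 4, adding deaths and the ceiling.** Step 2 flatters the gain, because deaths add QALY variance that baseline EQ-5D does not explain. With mean utility 0.80, scores capped at 1 and 24-month mortality of 4-8%:

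- Capping reduces the SD from 0.15-0.20 to about 0.14-0.17, so a one-SE imbalance is 0.020-0.025.
- The shift in the two-year increment is about 0.014-0.035 QALY.
- The SE of the unadjusted increment is 0.036-0.054, so the shift is about 0.3-0.7 of one SE.
- Adjustment reduces that SE by about 6-30%.

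Step 4 is the range to rely on. For scale only: averting 2 deaths per 100, spread evenly over two years (one year gained on average), at utility 0.8, is worth 0.02 × 1 × 0.8 = 0.016 QALY.

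**The case against.** The plan is silent on adjustment; it does not rule it out. An adjusted difference between arms would also fit the SAP's wording. This stands, so the point is an omission to fill and not a wrong method chosen.

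The QALY area formula is not written in either document, so the direct weight of 0.25 year rests on an inference. This stands too. The case does not depend on it alone, because baseline EQ-5D is expected to predict later EQ-5D under any construction from these visits. The missing formula is itself a gap.

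Under randomization, chance imbalance is ordinary sampling error, and the plan already carries uncertainty through probability intervals, a Bayesian bootstrap if costs are skewed, and sensitivity analyses. That is correct on average. What remains is error conditional on the observed imbalance, and lost precision.

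A reader might infer that a baseline imbalance could reverse the cost-effectiveness conclusion. The documents do not support that. They give no expected QALY or cost difference, no ceiling ratio and no size for the analysis set. The shift computed here is less than one standard error of the increment, and a long-term projection model is planned besides the within-trial ratio.

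**Conclusion.** The concern holds as a free improvement to a secondary economic endpoint. The SAP names no adjustment of the QALY increment for a baseline measure that the trial already collects. The unadjusted estimate is not biased on average. Under the Step 4 assumptions a typical chance imbalance moves it by about 0.014-0.035 QALY, and adjustment removes that shift and cuts the standard error by about 6-30%. All of the SD, correlation, mortality and sample-size inputs are assumptions, and the gain depends strongly on the correlation and on mortality. The primary result is not affected.

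**What to change.** In SAP 6.5.2.7:

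1. Estimate the within-trial QALY increment by regressing patient-level QALYs on arm and baseline EQ-5D, optionally with the TR-severity stratum, inside the same bootstrap as costs. Use the adjusted increment in the ICER, the net health benefit and their intervals. Report the unadjusted increment as a sensitivity analysis.
2. State how QALYs are built: instrument, value set, interpolation, treatment of death, the role of the baseline value, and the discount rate.
3. Give a rule for missing baseline EQ-5D. SAP 6.2.1 says missing baseline values are not imputed, so regression on baseline would otherwise drop randomized patients. Mean imputation of the covariate, without regard to arm, would do as a stated exception. If baseline also enters the QALY itself, that use needs its own rule; SAP 6.2.3 already allows multiple imputation for specific analyses.
4. Reconcile the US restriction in the protocol's Economic Measures section with the North American wording in the cost analysis text of both documents.

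The cost is a few sentences of SAP text, before data lock, when the SAP permits revision. No added data, visits or patients are needed.
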